### 5.6.2. Adverse Events Missing Data Rules:

For adverse events with unknown intensity (severity) or unknown relationship to study treatment, these will be imputed as follows:

- If the intensity (severity) of an adverse event is unknown/missing, the intensity will be imputed for the summary of adverse events as being the highest intensity that is not immediately life-threatening or resulting in death, i.e. “Severe”.
- If the relationship to investigational product of an adverse event is unknown/missing, and the adverse event onset occurred after first dose, or if onset date/time is unknown and it cannot be determined if onset occurred prior to dosing the relationship will be imputed for the summary of adverse events as related.

For adverse events, where either the onset time or resolution time is unknown, time since first dose and duration will be imputed as follows:

- If onset date is unknown, and it cannot be confirmed that onset was prior to the start of dose administration, then the AE will be classified as treatment-emergent, with unknown time since first dose.

- If either the date of onset or the date of resolution is unknown, then duration will be shown as unknown.
- If onset time is unknown:
  - If the date of onset is known to be the date of first dose administration, and it is confirmed by a CRF comment or communication with the site that onset was prior to the start of dose administration, then the AE will be classified as not treatment-emergent.
  - If the date of onset is known to be same as the date of first dose administration, and it is confirmed by a CRF comment or communication with the site that onset was after the start of dose administration, then the AE will be classified as treatment-emergent and the time since first dose will be shown on the listing as “<1” day.
  - If the date of onset is known to be later than the date of first dose administration, then Time since first dose will be determined as the number of days since first dose, shown on the listing as “~n” days, where n is the number of days difference between the date of dose administration and the date of onset.
- If either the onset time or resolution time is unknown:
  - If the date of onset and the date of resolution are known to be the same, then Duration will be shown on the listing as “<1” day.
  - If the date of onset and the date of resolution are known and are different, then Duration will be determined as the number of days difference between the date of onset and the date of resolution, shown on the listing as “~n” days.

### 5.6.3. Baseline for safety assessments:

- Missing values for safety assessments will not be imputed. If change from baseline is to be determined and the pre-dose baseline assessment is missing, then the previous scheduled result (e.g. Screening) will be used as the baseline. However, if the baseline is missing due to technical reasons and a subsequent unscheduled pre-dose assessment is used to confirm eligibility, this unscheduled assessment may be used as baseline.

### 5.7. Use of Abbreviations

Any abbreviations used in data listings will be included in the key in a footnote, as appropriate.

## 6. ANALYSIS POPULATIONS

### 6.1. Intent-to-Treat (ITT) Population

All randomized subjects who received at least one dose of study medication will be included in the ITT population. Subjects will be analysed according to the treatment they are planned to receive according to the randomization schedule. The ITT population will be used for the analysis and presentation of all efficacy data.

## 6.2. Per-Protocol (PP) Population

Subset of the ITT population consisting of subjects who 1) meet all inclusion/exclusion criteria that would affect the treatment evaluation, 2) apply  $\geq 80\%$  but  $\leq 120\%$  of the planned doses of study treatment, 3) who had a VIIS measurement at Visit 6 (EOS), and 4) have no major protocol violations that would affect the treatment evaluation. Subjects will be analysed according to the treatment they are planned to receive according to the randomization schedule. All efficacy data will be analysed using the PP population.

## 6.3. Safety Population

All subjects randomly assigned to study treatment and who take at least 1 dose of study medication will be included in the Safety Population. Subjects will be analysed according to the treatment they actually receive. Safety data will be presented for all subjects in the safety analysis set and summarised by dose level / treatment group.

Subject disposition and background data, including demographics, relevant background and participation data, will be presented for all subjects in the safety analysis set.

Subjects who are assigned a randomization number but withdraw prior to dosing will not be included in the safety analysis set. Available details of their participation and reason for withdrawal will be listed separately.

## 7. SUBJECT DISPOSITION/BACKGROUND DATA

### 7.1. Subject Disposition

Subject disposition and administration procedures recorded in the CRF are as follows:

- Written informed consent
- Randomization
- Administration of IP
- Study completion /discontinuation
- Protocol deviations
- Additional comments

Details of participation and inclusion in analysis populations will be listed by subject. Completion status will be summarised by dose level / treatment group.

Details of administration of IP will be listed by subject. Exposure to IP will be summarised by dose level / treatment group. Descriptive statistics will be used to summarize study treatment compliance for the ITT population. A subject will be considered compliant with the dosing regimen if the subject applies at least 80% but no more than 120% of the expected number of applications or dose.

Protocol deviations will be listed by subject.

Screen failures will be listed by subject. Demography, screen failure details, eligibility criteria, and any SAEs will be listed for screen failures.

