6.4 Study Treatment Compliance

The prescribed dosage, timing, and mode of administration may not be changed, except as defined in [Section 7.4](#). Any departures from the intended regimen must be recorded in the eCRFs.

During the course of the study, compliance to study drug application will be evaluated via Subject diaries and accountability by the site, including weighing the tubes. Subjects exhibiting poor compliance should be counseled on the importance of good compliance to the study dosing regimen.

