6.6 Dose Regimen Modification

Dose regimen modification is not allowed in this study, except for a structured treatment interruption scheme (drug holiday) as detailed in [Section 7.4](#).

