8.1.4 Visit 6 (End of Study)

The EOS visit will occur at Week 12 on Day 85 \pm 7 days. Any subject who is discontinued from study prior to Visit 6 (EOS) should complete the procedures listed for EOS during their last study visit or Early Termination visit. This visit may be performed either on site or as a remote visit, although all efforts should be made for an on-site visit.

The following will be completed at this visit:

- The subject will be queried for any changes in health status since the previous visit, including concomitant medications and concurrent procedures/therapies. Any AEs will be recorded.
- Age-appropriate DLQI and I-NRS will be completed by the subject.

- Abbreviated physical examination/ subject disposition via directed query, vital signs, clinical laboratory tests
- Photography (select study sites and for all subjects where this visit will be conducted remotely)
- UPT for WOCBP will be performed
- The study staff will perform the clinical evaluations , including local skin reactions and record the percent BSA with CI in the Treatment Area and VIIS Assessment Areas
- VIIS for Scaling will be performed for the VIIS Assessment Area and IGA for Scaling and Fissure will be performed for the Treatment Area.
-
- Study treatment accountability will be performed, including weighing of all returned tubes.
- The Subject Diary will be collected and reviewed.

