9.3 Populations for Analyses

For purposes of analysis, the analysis sets are defined in [Table 6](#).

Table 6 Analysis Sets

Analysis Set	Description
Intent-to-Treat (ITT) Population	All randomized subjects who received at least one dose of study medication . Subjects will be analyzed according to the treatment they are planned to receive according to the randomization schedule.
Per-Protocol (PP) Population	Subset of the ITT population consisting of subjects who 1) meet all inclusion/exclusion criteria that would affect the treatment evaluation, 2) apply $\geq 80\%$ but $\leq 120\%$ of the planned doses of study treatment, 3) who had a VIIS measurement at Visit 6 (EOS), and 4) have no major protocol violations that would affect the treatment evaluation. The final definition of the PP population will be presented in the SAP. Subjects will be analyzed according to the treatment they are planned to receive according to the randomization schedule.
Safety Population	All subjects randomly assigned to study treatment and who take at least 1 dose of study medication. Subjects will be analyzed according to the treatment they actually receive.

Abbreviations: ITT = intent-to-treat; PP = per-protocol; SAP = Statistical Analysis Plan.

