9.4.6 Dosing Compliance

Descriptive statistics will be used to summarize study treatment compliance for the ITT population. A subject will be considered compliant with the dosing regimen if the subject applies at least 80% but no more than 120% of the expected number of applications or dose.

Measures of overall study treatment compliance will include the duration of treatment (number of days dosed), the total number of applications (determined from the actual number of applications reported by the subject), quantity of dose, and the percent of expected doses applied. A subject will be considered compliant with the dosing regimen if the subject applies at least 80% but no more than 120% of the expected number of applications or dose.

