Table 14.2.1.10.2	Visual Index for Ichthyosis Severity – Success Rate by drug/BSA ratio (PP)
Table 14.2.1.11.1	Visual Index for Ichthyosis Severity – Success Rate by drug/BMI ratio (ITT)
Table 14.2.1.11.2	Visual Index for Ichthyosis Severity – Success Rate by drug/BMI ratio (PP)
Table 14.2.1.12.1	Visual Index for Ichthyosis Severity – Success Rate by drug/kg ratio (ITT)
Figure 14.2.1.12.1	Visual Index for Ichthyosis Severity – Success Rate by drug/weight ratio (ITT)
Table 14.2.1.12.2	Visual Index for Ichthyosis Severity – Success Rate by drug/kg ratio (PP)
Figure 14.2.1.12.2	Visual Index for Ichthyosis Severity – Success Rate by drug/weight ratio (PP)
Table 14.2.1.13.1	Visual Index for Ichthyosis Severity – Success Rate by OTC Steroid Cream (ITT)
Table 14.2.1.13.2	Visual Index for Ichthyosis Severity – Success Rate by OTC Steroid Cream (PP)
Table 14.2.1.14.1	Visual Index for Ichthyosis Severity – Success Rate by assessment medium (ITT)
Table 14.2.1.14.2	Visual Index for Ichthyosis Severity – Success Rate by assessment medium (PP)
Table 14.2.1.15.1	Visual Index for Ichthyosis Severity – Success Rate by VIIS Body Region (ITT)

Table 14.2.1.15.2	Visual Index for Ichthyosis Severity – Success Rate by VIIS Body Region (PP)
Table 14.2.1.16.1	Visual Index for Ichthyosis Severity – Success Rate by BSA Stratification (ITT)
Table 14.2.1.16.2	Visual Index for Ichthyosis Severity – Success Rate by BSA Stratification (PP)
Table 14.2.1.17.1	Changes from Baseline in VIIS score, Active Vs Vehicle – MMRM analysis (ITT)
Table 14.2.1.17.2	Changes from Baseline in VIIS score, Active Vs Vehicle – MMRM analysis (PP)
Table 14.2.1.18.1	Visual Index for Ichthyosis Severity – Non-Target Sites Success Rate (ITT)
Table 14.2.1.18.2	Visual Index for Ichthyosis Severity – Non-Target Sites Success Rate (PP)
Table 14.2.1.19.1	Visual Index for Ichthyosis Severity – Success Rate by Drug Interruption (ITT)
Table 14.2.1.19.2	Visual Index for Ichthyosis Severity – Success Rate by Drug Interruption (PP)
Table 14.2.2.1.1	Investigator’s Global Assessment – Change From Baseline (ITT)
Table 14.2.2.1.2	Investigator’s Global Assessment – Change From Baseline (PP)
Table 14.2.2.2.1	Investigator’s Global Assessment – Shift Table (ITT)
Table 14.2.2.2.2	Investigator’s Global Assessment – Shift Table (PP)
Table 14.2.2.3.1	Investigator’s Global Assessment – Success Rate (ITT)
Figure 14.2.2.3.1	Investigator’s Global Assessment – Success Rate (ITT)

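### Does the undefined dosing denominator behind the 80% to 120% per-protocol limit need to be settled in the SAP?

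*SAP*

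**What the plan says.** Protocol Table 6 (section 9.3) lists four PP criteria and adds: "The final definition of the PP population will be presented in the SAP". SAP 6.2 repeats the four criteria without further detail. The second requires 80% to 120% "of the planned doses of study treatment, 3) who had a VIIS measurement at Visit 6 (EOS"). SAP 7.1 has a parallel rule for the descriptive compliance summary: a subject complies who "applies at least 80% but no more than 120% of the expected number of applications or dose". SAP 5.5, which lists derived data, contains no compliance derivation. Protocol 9.4.6 describes the measures as a total number of applications ("determined from the actual number of applications reported by the subject), quantity of dose, and the percent of expected doses applied"), but does not say how the expected number is built.

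The protocol permits one kind of departure from twice-daily dosing. Section 6.4 states: "The prescribed dosage, timing, and mode of administration may not be changed, except as defined in" Section 7.4. Section 6.6 states: "Dose regimen modification is not allowed in this study, except for a structured treatment interruption scheme (drug holiday"). Under 7.4, treatment restarts once daily for two weeks after the reaction resolves; the synopsis caps an interruption at two weeks. Section 6.4 also requires departures from the intended regimen to be recorded in the eCRF.

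A subject who leaves early "should complete the procedures listed for EOS during their last study visit or Early Termination visit" (protocol 8.1.4). SAP 9.2 makes ITT primary. SAP Appendix 2 plans PP versions of the efficacy tables, including VIIS "Success Rate by Drug Interruption (PP").

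**The concern.** The protocol defers the definition and the SAP hands it back unchanged, with two different undefined terms: planned doses in 6.2, and expected applications or dose in 7.1. A subject who follows the interruption scheme exactly makes fewer applications than the full twice-daily course. Whether those applications still count as planned decides whether the subject is in PP.

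If this mattered, it would matter in the PP analyses: 48 of the 100 efficacy tables in Appendix 2, including the PP analysis of the primary endpoint. With about 15 subjects per arm, a few reclassified subjects are a visible share. An undefined rule also leaves room to choose the denominator with results in view. Early stoppers add to the worry. They may have an end-of-study VIIS through an early termination visit, which leaves the dosing limit as the only numeric screen.

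**Working it through.** The documents state no compliance percentage, so there is no planned figure to reproduce. The check counts applications.

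**Inputs**

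- Course: 12 weeks = 84 days (protocol 4.1; SAP 4.3), twice daily (protocol 6.1).
- Longest single interruption: 14 days (synopsis; 7.4 requires permanent discontinuation if the reaction has not resolved after two weeks off).
- Restart: 14 days once daily (7.4).
- Visit 6: Day 85 ± 7 (protocol 8.1.4).
- Limits: 80% to 120%.

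**1. Full course.** 84 × 2 = 168 applications. 80% of 168 = 134.4, so at least 135 are needed.

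**2. One full interruption, completed restart, no other missed dose.** Applied = 168 − 2 × 14 − 14 = 126.

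| Denominator | Calculation | PP criterion 2 |
|---|---|---|
| Fixed course | 126/168 = 75.0% | fails |
| Off days removed | 126/(168 − 28) = 126/140 = 90.0% | passes |
| As prescribed | 126/126 = 100% | passes |

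**3. Where the reading starts to matter.** For D days off on an 84-day course with a completed restart, the fixed share is (168 − 2D − 14)/168.

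- D = 9: 136/168 = 80.95%, passes.
- D = 10: 134/168 = 79.8%, fails.
- With off days removed, every D from 1 to 14 gives 90.0% to 91.6%.

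So the three readings disagree only for D = 10 to 14.

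**4. Exceptions within that range, on a fixed 168.**

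- Late interruptions cut the restart short. Ten days off from Day 62 leaves 13 once-daily days: 61 × 2 + 13 = 135, and 135/168 = 80.4%. Fourteen days off from Day 66 leaves 5: 65 × 2 + 5 = 135, again 80.4%. Both pass.
- Course length T moves the count. With 14 days off and a completed restart, applied = 2T − 42. T = 77 gives 112/168 = 66.7%; T = 88 gives 134/168 = 79.8%; T = 89 gives 136/168 = 80.95%; T = 91 gives 140/168 = 83.3%. From 89 days the subject passes.
- If the denominator instead follows actual duration with off days kept (2T), the share is 112/154 = 72.7% at 77 days and 140/182 = 76.9% at 91 days, below 80% at both ends of the window.

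**5. A subject told to interrupt who keeps applying twice daily.** 168/168 = 100% (fixed), 168/140 = 120.0% (off days removed, at the limit), 168/126 = 133.3% (as prescribed, fails).

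**6. Permanent stop after 14 twice-daily days and 14 unresolved days off.** Applied = 28. Against the fixed course, 28/168 = 16.7%. With off days removed but the remaining 56 days kept at twice daily, 28/(28 + 112) = 28/140 = 20.0%. Only if all later days are dropped does it become 28/28 = 100%.

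**7. Size in an arm of 15.** The documents give no interruption rates. As an assumption, 0 to 4 reclassified subjects would be 0% to 4/15 = 26.7% of an arm; one subject is 1/15 = 6.7%.

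Two interruptions are not worked through. Section 7.4 allows a second interruption but requires permanent discontinuation if reactions recur on twice-daily dosing, and those provisions would have to be reconciled first.

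**The case for a change.** The best case for a change is that the SAP was the appointed place for this definition and does not give it. The interruption scheme is the protocol's own, so its use is foreseeable, and one sentence would settle the matter. Neither document describes a blinded review at which the denominator would be fixed. The study is meant to assist dose selection for Phase 3, and a PP set chosen late could colour that. The planned PP tables by interruption duration would also show or omit longer interruptions according to the reading.

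What stands is that the text is silent, and that for a 10 to 14 day interruption the silence can decide membership. The rest is weaker:

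- The readings are not equally open for PP. SAP 6.2 speaks of planned doses, and the plan is twice daily for 12 weeks, so the fixed course is the more natural reading though not an explicit one. The looser wording in SAP 7.1 governs only a descriptive compliance summary.
- Diary counts are the obvious numerator for a criterion about doses, since protocol 9.4.6 takes application counts from the subject's report. Grams against applications is a minor question here.
- The 100% score for an early stopper requires deleting all untreated later days from a count of planned doses, which the wording does not invite. The criterion on major protocol violations also applies, although a permitted stop need not be one.
- The subject who ignores an instruction to interrupt is a contrived case, and that same criterion could exclude them.
- The 48 tables measure output, not effect: each has an ITT counterpart. The tables by interruption are exploratory and planned only if the data allow.

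**Conclusion.** No change follows. This is missing detail that the analysts have to supply in order to program the PP flag. No stated rule gives a wrong answer. A fixed course measures exposure to the full regimen; an adjusted course measures adherence to what was prescribed. Both are defensible.

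The consequence is bounded. The reading matters for a single interruption of 10 to 14 days, on about 84 treated days, with a completed restart and otherwise perfect adherence. It touches only the supportive PP analyses and the compliance label. The ITT analysis of VIIS-50, on which the plan rests, is the same under every reading, in a study that SAP 4.5 describes as having no formal power calculation.

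The choice will also be visible. The SAP plans listings of population membership by subject (16.2.3.1), compliance (16.2.5.2) and drug interruption details (16.2.5.3), so a reader can see who was left out and apply the other denominator. A second PP run and an exclusion table would summarise what those listings already show.

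This conclusion rests on ITT remaining primary and on the denominator being applied uniformly across arms. How many subjects would change status is unknown and may be none.

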## 7.2. Baseline and Eligibility Assessments

Baseline and eligibility assessments are as follows:

- Demographic details
- Medical and surgical history
- Physical examination
- Eligibility
- Genetic testing
- Serology (HIV)
- Urine pregnancy tests
- Assessments at screening and up to pre-dose baseline of safety assessments performed throughout the study, including physical examinations and vital signs

## 7.3. Baseline Data Analysis

Demographic and Baseline characteristics will be summarized by treatment group for the Safety, ITT, and PP populations. Frequency counts and percentages will be reported for categorical data and sample size, mean, median, standard deviation (SD), minimum (min), and maximum (max) will be reported for the continuous variables.

## 8. SAFETY DATA

### 8.1. Safety Assessments

Safety assessments are as follows:

- Adverse events and concomitant medications used:
  - Continuous monitoring throughout the study period
- Vital signs including temperature, systolic and diastolic blood pressure, heart rate, and respiration rate will be measured at Visit 1 (Screening) and Visit 6 (EOS).
- Clinical laboratory tests:
  - Clinical Chemistry: Blood Urea Nitrogen, Creatinine, Glucose (Fasting), Potassium, Sodium, Calcium, Aspartate aminotransferase (AST)/ Serum Glutamic-Oxaloacetic Transaminase (SGOT), Alanine aminotransferase (ALT)/Serum Glutamic-Pyruvic Transaminase (SGPT), Alkaline Phosphatase, Total and Direct Bilirubin and Total Protein
  - Hematology: Platelet Count, Red Blood Cell (RBC) Count, Haemoglobin, Hematocrit, Mean Corpuscular Volume (MCV), Mean Corpuscular Hemoglobin (MCH), % Reticulocytes, lymphocytes, monocytes, eosinophils, basophils, neutrophils
  - Routine Urinalysis: Specific Gravity, pH, Glucose, Protein, Blood, Ketones, (Bilirubin, Urobilinogen, Nitrite, Leukocyte Esterase) by Dipstick, Microscopic Examination (if Blood or Protein Is Abnormal)

- Serology: human immunodeficiency virus [HIV] Antibody
- Drug and alcohol screen: Opiates, methadone, cocaine, amphetamines (including ecstasy), cannabinoids, barbiturates, benzodiazepines, tricyclic antidepressants, and alcohol
- Pregnancy test (Women of Childbearing Potential): Urine Human Chorionic Gonadotropin (hCG) Pregnancy Test
- Physical examination: A brief physical examination will be performed at Visit 1 (Screening). Abbreviated examination/ subject disposition will be conducted at Visit 2 (Baseline) to identify any changes since the Screening visit and at Visit 6 EOS to assess for any changes during the study. The examination will evaluate head and neck, dermatological, cardiovascular, respiratory, gastrointestinal (abdomen), and gross motor and gait body assessments. Abnormalities at Visit 1 (Screening) and Visit 2 (Baseline) prior to treatment will be recorded as medical history. Any new or worsening abnormalities at Visit 6 (EOS) will be recorded as AEs.
- Local Skin Reactions (LSRs) known to be associated with retinoids (burning/stinging, erythema, erosions, and edema) or other causes regardless of blinded causality assessment within the areas treated with study medication will be evaluated at every study visit (except Screening), using a 4-point ordinal scale where 0 = none, 1 = mild, 2 = moderate, and 3 = severe.

